5.5 Rounding

In listings, data will be presented with the same precision as the original data; at the output creation stage, derived data will be rounded for presentation purposes.

For all summaries, the standard deviation will be presented to two decimal place greater than the original data, the mean and median will be presented to one decimal place greater than the original data and the minimum and maximum will be presented to the same number of decimal places as the original data.

For calculation of the proportion, one decimal place will be presented.

The rounding will be performed to the closest integer/first decimal using the common mid-point between the two consecutive values (e.g. 5.0 to 5.4 will be rounded to an integer of 5, and 5.5 to 5.9 will be rounded to an integer of 6)

5.6 Analysis Populations

- The All subjects screened will include all subjects during screening evaluations.
- The Safety population will include all subjects who receive any amount of Alpha-1 MP.
- The PK population (GTI1401 only) will include all subjects who receive Alpha-1 MP dose and have sufficient samples to calculate the PK parameters.

5.7 Denominator

Unless otherwise mentioned, denominator of percentage in each table will be the number of population designated in each table.

6 Subject Disposition Subject Disposition

6.1 Summary Table of Subject Disposition	
Population	: All subjects screened
Contents	: 
• The number of all subjects screened• The number of all subjects dosed with Alpha-1 MP (Safety population)

6.2 Summary Table of Subjects Who Discontinue from the Study	
Population	: Safety population
Contents	: 
• The number and percentage of subjects who complete the study• The number and percentage of subjects who discontinue from the study by reason for discontinuation

Disposition status will be listed for all subjects. A listing will also be provided for screening failure subjects.

7 Protocol Deviations

7.1 Summary Table of Protocol Deviations	
Population	: Safety population
Contents	: 
The number and percentage of deviations by type and severity will be summarized. Deviations from the protocol will be identified during the study and discussed in the data review meeting. Protocol deviation is defined in “GTI1401 and OLE Protocol Deviation Guidance_24Oct2016_Biling_Clean.pdf”
 
Listing of all deviation.

8 Demographics

8.1 Summary Table of Demographics		
Population	:	Safety population
Contents	:	
For continuous variables, mean, standard deviation, median, and minimum/maximum will be provided. For categorical/qualitative data, frequency counts will be provided (For pregnancy status, the percentage of population is not included).
 
Listing of following contests is provided separately.
 
 Demographics (including alpha₁- Antitrypsin Deficiency history) Smoking history Medical history
Analysis variables	:	Contents, category and digit to be displayed are showed in the following table.

Contents	Category	Digits to be displayed
Sex	Male Female	
Age [years]		Integer
Race	Asian	
Weight [kg]		1 decimal place
Height [cm]		1 decimal place
Pregnancy status	NA (Males are included in this category) Negative Positive	
Smoking status	Never Former (>100 cigarettes or equivalent of tobacco in subject's lifetime) Current (not eligible for study)	
Total alpha ₁ -PI serum level at time of diagnosis [mg/dL]		1 decimal place
Time since First Diagnosis of alpha ₁ -Antitrypsin Deficiency [years]		1 decimal place
Best FEV ₁ [L] at Baseline		2 decimal place
Best FVC [L] at Baseline		2 decimal place
FEV ₁ Predicted [%]	0=<< 30 30=<< 70 70=<<100	
FEV ₁ Predicted [%]		1 decimal place
15th Percentile of lung Density [g/L]		1 decimal place
Mean lung density [g/L]		1 decimal place

9 Treatments and Medications

9.1 Prior and Concomitant Medications

Definition of prior medication and concomitant medication for GTI 1401

Prior medications are defined as any medication which ended before the first infusion of study drug of GTI 1401.

Concomitant medications are defined as any medication which is started on or after the first infusion of study drug of GTI 1401 or any medication taken prior to the first infusion of study drug of GTI 1401 and continued after the first infusion of study drug of GTI 1401.

Definition concomitant medication for GTI 1401-OLE

Concomitant medications are defined as any medication which is started on or after the first infusion of study drug of GTI 1401-OLE or any medication taken prior to the first infusion of study drug of GTI 1401-OLE and continued after the first infusion of study drug of GTI 1401-OLE.

9.1.1 Summary Table of Prior and Concomitant Medication		
Population	:	Safety population
Contents	:	
Summaries of all medications taken during the course of the study will be presented in tabular form and coded using ATC classification codes via the World Health Organization Drug classification Dictionary (WHO-DD). All medications will be summarized and sorted alphabetically by medication class (i.e., ATC level 2) and medication sub-class (i.e., ATC level 4). If the ATC level 4 term is missing, the ATC level 3 term will be used in the medication summary table and data listing.
 
For the summary tables, if a subject has taken a concomitant medication more than once, the subject will be counted only once.
 
All medications will be listed by subject. New medications starting after the first infusion will be indicated if the medication start date relative to the first study drug infusion is greater than 0 in the subject data listing.

9.2 Extent of Exposure

9.2.1 Summary Table of Drug Exposure	
Population :	Safety population
Contents :	
Following contents regarding to exposure information are summarized. Digits to be displayed are showed in Table A
 
 • Treatment duration [Week] • Number of infusions received • Total volume infused [mL] • Volume infused per week [mL] • Infusion duration [Minute] 
Treatment duration in weeks is calculated as:
 $(TheLastDoseDate - TheFirstDoseDate + 7) / 7$ 
Volume infused per week is calculated as:
 $the\ Total\ Volume\ Infused\ [mL] / the\ Treatment\ Duration\ [Week]$ 
Infusion Duration is calculated as:
 $the\ Infusion\ Stop\ Time\ [HH:MM] - the\ Infusion\ Start\ Time\ [HH:MM] + 1$ 
For Infusion Duration, the summary statistics will be calculated for mean duration of each week.
 
A list will be provided for Alpha-1 MP dose, volume prepared, and volume infused.

Table A:

Contents	Digits to be displayed
Treatment duration [week]	1 decimal place
Number of infusions received	Integer
Total volume infused [mL]	1 decimal place
Volume infused per week [mL]	1 decimal place
Infusion duration [minute]	Integer

9.2.2 Summary Table of Infusion Interruptions		
Population	:	Safety population
Contents	:	The number and percentage of infusion with interruptions will be summarized by analysis visit. Reasons for interruptions will be displayed in the listings.

9.3 Treatment Compliance

Treatment compliance will be calculated as:

$$\frac{\text{TotalVolumeInfused}}{\text{TotalVolume Prepared}} \times 100\%$$

The total volume prepared is collected on the eCRF and is calculated based on the subject's weight at baseline.

The total volume prepared and dispensed by pharmacist is the intended dose volume a subject should be given based on the body weight.

Infusion compliance will be calculated as:

$$\frac{\text{The Number of Actual Infusions}}{\text{The Number of Infusions Expected}} \times 100\%$$

For subjects who drop out from the study early, the number of infusions expected will depend on the number of weeks the subjects are in the study.

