9.3.1 Summary Table of Treatment Compliance		
Population	:	Safety population
Contents	:	
Following contents will be displayed.
 
 • Summary of treatment compliance [%] • The number of subjects with treatment compliance $\geq 80\%$ • Summary of infusion compliance [%] 
A listing of treatment compliance will be provided.

10 Exploratory Analysis

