10.1 PK Analysis

Alpha₁-Proteinase Inhibitor (alpha₁-PI) concentrations in serum will be measured by validated content assay. The concentration data will be presented and summarized. Time points recorded on CRF will be used as analysis time points.

Time Table for Week 8 and Week 9

Visit	Actual elapsed time (real-time)	Nominal time point (numeric version) (hours)	Scheduled time point
Week 8	0	0	Immediately before the intravenous infusion
Week 8	0.30	0.25	Immediately after the intravenous infusion (after flushing the infusion line with physiological saline) (at 0 hours)
Week 8	0.55	0.5	15 minutes after completion of the intravenous infusion
Week 8	2.35	2.25	2 hours after completion of the intravenous infusion
Week 8	4.67	4.25	4 hours after completion of the intravenous infusion
Week 8	8.67	8.25	8 hours after completion of the intravenous infusion
Week 8	26.02	24.25	24 ± 4 hours (1 day after completion of the intravenous infusion)
Week 8	49.17	48.25	48 ± 4 hours (2 days after completion of the intravenous infusion)
Week 8	120.58	120.25	120 hours ± 1 day (5 days after completion of the intravenous infusion)
Week 9	169.50	168.25	168 hours ± 1 day (7 days after completion of the intravenous infusion) (Week 9)

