10.1.1 Summary Table of Alpha ₁ -PI Concentrations (GTI1401 only)		
Population	:	PK population
Contents	:	Alpha ₁ -PI concentrations will be summarized. The summaries will include n, mean (SD), coefficient of variation (%CV) (=SD/Arithmetic mean), median, minimum, maximum as well as geometric mean.
Digit	:	2 decimal places will be displayed for summary table of alpha ₁ -PI Concentrations.
Analysis visit	:	
• Immediately before the intravenous infusion• Immediately after infusion completion (after sodium chloride [NaCl] flush) (0 hour)• 15 minutes after infusion completion• 2 hours after infusion completion• 4 hours after infusion completion• 8 hours after infusion completion• 24±4 hours (1 day after infusion completion)• 48±4 hours (2 days after infusion completion)• 120 hours ± 1 day (5 days after infusion completion)• 168 hours ± 1 day (7 days after infusion completion) (Week 9 Visit) 
Serum concentrations of alpha₁-PI determined by content assay will be presented in a listing by subject, study week, and scheduled or nominal time point.
 
This data listing will provide details of all planned plasma collection time points (scheduled and nominal times as specified in Section 12.1), actual collection date and clock times and elapsed times from the start of the study drug infusion, as well as alpha₁-PI concentrations. Samples excluded from PK analysis will be flagged.
 
The date/clock time for the start and completion of study drug infusion, the actual volume infused, and the actual dose infused (mg/kg) at Week 8 (PK assessment visit) will be presented in a separate listing.

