- c: Subjects not entering the extension trial (GTI1401-OLE) and subjects who receive Alpha-1 MP at any dose and discontinue this clinical trial early will be asked to return to the study center for the follow-up/study completion procedures and evaluations scheduled at the Week 12 visit. This visit should be made at the timing as close as possible to 4 weeks (i.e., 30 days) after the last dose of the investigational drug in the subject.
- d: CT densitometry scan should be performed anytime from the Screening Visit to the Week 1 (Baseline) Visit; if the CT densitometry scan is performed at the Week 1 (Baseline) Visit, then it must be performed prior to the first Alpha-1 MP infusion. This CT scan will measure lung density.
- e: Body weight will be used to calculate the Alpha-1 MP dose, and this recorded body weight will be used for dose calculation until the next scheduled body weight measurement.
- f: Blood samples for viral safety assessment (viral NAT and viral serologic test) will be collected before the intravenous infusions of Alpha-1 MP at the Week 1 (baseline) visit. However, the collected samples will be tested only if the subject shows clinical signs or symptoms suggestive of viral infection during the trial period. Only in this case will additional blood samples for viral NAT and viral serologic test be collected. All these collected blood samples will be stored until completion of all the tests in this clinical trial (GTI1401) and the extension trial (GTI1401-OLE).
- g: Sampling will be performed before each intravenous infusion of Alpha-1 MP.
- h: Vital signs will be checked immediately before and after each intravenous infusion of Alpha-1 MP.
- i: Pulmonary function tests after administration of a bronchodilator will be performed 15 to 30 minutes after administration of a bronchodilator. For a short-acting bronchodilator, subjects will receive 4 puffs of salbutamol given by an MDI and spacer in each pulmonary function testing. The same bronchodilator as that used at the start of the trial should be used throughout the trial period.
- j: Sampling will be performed in subjects with no previously documented alpha1-PI levels as measured by nephelometry (if it is unknown whether the subject's alpha1-PI level is <50 mg/dL or not).

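### SAP 9.2.1 adds one minute to every infusion duration by putting + 1 on a difference of clock times; the weight wording in 9.3 also needs reconciling with the appendices

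*SAP*

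**What the plan says.** **Infusion duration.** In SAP 9.2.1 (Summary Table of Drug Exposure), the line "Infusion Duration is calculated as" is followed by stop time in HH:MM minus start time in HH:MM, plus 1. Table A shows the result in minutes, as an integer. Section 10.1.1 separately promises a listing for the Week 8 PK visit: "The date/clock time for the start and completion of study drug infusion", together with the volume and dose actually infused.

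**Volume prepared.** Section 9.3 defines treatment compliance as total volume infused over total volume prepared. On the denominator it says: "The total volume prepared is collected on the eCRF and is calculated based on the subject's weight at baseline". Its next sentence says that what the pharmacist prepares and dispenses "is the intended dose volume a subject should be given based on the body weight", with no mention of baseline. Section 9.2.1 treats the same quantity as a data item: "A list will be provided for Alpha-1 MP dose, volume prepared, and volume infused".

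**Weight schedule.** Appendix 1 footnote e says that "this recorded body weight will be used for dose calculation until the next scheduled body weight measurement". The body weight row of Appendix 1 carries that footnote at Week 1 and again at Week 5. Appendix 2 marks weight at the quarterly visits of the extension (Ext Weeks 12, 24, 36 and 48).

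**The concern.** Adding 1 is right for an inclusive count of calendar days, where the first and the last day both count. It is not right for the time between two clock readings: an infusion from 10:00 to 10:15 lasts 15 minutes, not 16. The SAP gives no reason for the extra minute. At stake is a small but systematic error in a table that will go into the study report. It can be seen by anyone who subtracts the Week 8 clock times in the listing. With as few as three subjects planned (5.4), that comparison is easy to make.

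The weight wording is a different kind of problem. Two parts of one document describe the basis of the prepared volume differently, and a reader cannot tell which describes what was done.

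**Working it through.** **1. Is the added constant justified?** Compare the two duration formulas in 9.2.1.

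- Treatment duration = (last dose date − first dose date + 7) / 7. For eight weekly infusions the dates span 49 days, and (49 + 7) / 7 = 8.0 weeks. The constant credits the week covered by the last dose, so it is sensible.
- Infusion duration = stop − start + 1. With D the true elapsed minutes, stop − start = D, so the formula returns D + 1. Nothing corresponds to the extra minute.

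**2. What scale applies?** The SAP states no infusion length outright, but the timetable in 10.1 implies one. Its zero is the sample taken just before the infusion, and 10.1.1 measures elapsed time from the start of infusion. The sample taken at the end of infusion, after the flush, stands at 0.25 h in the nominal column and 0.30 h in the actual-time column.

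- 0.25 × 60 = 15 minutes
- 0.30 × 60 = 18 minutes

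**3. Size of the error.**

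| Elapsed (min) | SAP formula (min) | Excess |
|---|---|---|
| 15 | 16 | 1/15 = 6.7% |
| 18 | 19 | 1/18 = 5.6% |

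The shift is constant, so the mean, median, minimum and maximum each rise by exactly one minute and the standard deviation does not change.

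**4. The weight passages side by side.**

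| Place | Basis given for the prepared volume or dose |
|---|---|
| 9.3, first sentence | Weight at baseline; value collected on the eCRF |
| 9.3, second sentence | Body weight, not limited to baseline |
| Appendix 1, footnote e | Latest scheduled weight, until the next one |
| Appendix 1, weight row | Footnote e at Week 1 and Week 5 |
| Appendix 2, weight row | Quarterly extension visits |

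The Week 5 position depends on column alignment in the schedule table. It is supported by the laboratory and urinary cotinine rows, which carry a mark in the same column and for which 11.2.1 and 11.5.1 name Week 5 as an analysis visit. On that reading, the baseline clause and footnote e disagree for the infusions at Weeks 5 to 8, which are 4 of the 8 in GTI1401. The later weights in Appendix 2 raise the same question for the extension.

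**5. Does the weight conflict change an output?** Neither term of the compliance ratio contains weight. If a subject receives all that was prepared and the recorded volumes are summed, infused / prepared = 100% whichever weight set the dose.

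**The case against.** The best defence of the + 1 is that times are recorded to the minute and that counting both the first and the last minute is a uniform convention, exactly reversible. That is possible, but the SAP does not say so, and the result would still disagree with its own Week 8 listing. What stands is that the consequence is small: no threshold, comparator or test uses this variable, and PK estimation uses actual sample times (5.1).

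Three stronger readings are tempting and are not supported.

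- *The PK timetable proves that the SAP elsewhere uses plain subtraction.* The row for "15 minutes after completion of the intravenous infusion" does sit exactly 15 minutes after the end-of-infusion row in both time columns. But that is an interval from completion to sample, to which the 9.2.1 rule does not apply, and in the nominal column the gap is there by design. The case against the + 1 rests on what a clock difference is.
- *The error can be scaled to 30- or 60-minute infusions.* Nothing in the SAP points to such lengths; its timetable points to about 15 to 18 minutes.
- *Compliance will be wrong.* A reader might infer that a fully dosed subject with an assumed 5% weight loss at Week 5 would show (4 + 4 × 0.95) / 8 = 97.5%. That needs a programmer to set aside the collected field and rebuild the denominator from baseline weight. The SAP specifies no such step and gives no conversion from mg/kg to mL. Section 9.3 already describes the denominator as collected on the eCRF, and "Summary of infusion compliance" in the same table (9.3.1) covers infusions that were never given.

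**Conclusion.** The infusion-duration formula is wrong as written. It overstates every duration by one minute, about 5.6% to 6.7% if infusions last the 15 to 18 minutes (flush included) that the PK timetable implies. The one-minute error holds for any infusion length; only the percentage rests on the timetable.

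The baseline-weight clause in 9.3 is an inconsistency of wording with Appendix 1 footnote e and with the later scheduled weights in both appendices. It is not a derivation error, and it leaves compliance unchanged when the recorded prepared volume is the denominator.

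Severity is minor. Only descriptive output is affected.

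**What to change.** 1. In 9.2.1, delete the + 1 from the infusion-duration formula. This changes one term in the SAP and one in the derivation code.
2. Reconcile the baseline-weight sentence in 9.3 with Appendix 1 footnote e and with the weight rows of Appendices 1 and 2. Which weight governs the dose is for the sponsor to settle. In the same edit, it would help to say outright that the compliance denominator is the prepared volume recorded on the eCRF, summed over infusions.

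Neither change needs new data or a new output.

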9.3.1 Summary Table of Treatment Compliance		
Population	:	Safety population
Contents	:	
Following contents will be displayed.
 
 • Summary of treatment compliance [%] • The number of subjects with treatment compliance $\geq 80\%$ • Summary of infusion compliance [%] 
A listing of treatment compliance will be provided.

10 Exploratory Analysis

10.1 PK Analysis

Alpha₁-Proteinase Inhibitor (alpha₁-PI) concentrations in serum will be measured by validated content assay. The concentration data will be presented and summarized. Time points recorded on CRF will be used as analysis time points.

Time Table for Week 8 and Week 9

Visit	Actual elapsed time (real-time)	Nominal time point (numeric version) (hours)	Scheduled time point
Week 8	0	0	Immediately before the intravenous infusion
Week 8	0.30	0.25	Immediately after the intravenous infusion (after flushing the infusion line with physiological saline) (at 0 hours)
Week 8	0.55	0.5	15 minutes after completion of the intravenous infusion
Week 8	2.35	2.25	2 hours after completion of the intravenous infusion
Week 8	4.67	4.25	4 hours after completion of the intravenous infusion
Week 8	8.67	8.25	8 hours after completion of the intravenous infusion
Week 8	26.02	24.25	24 ± 4 hours (1 day after completion of the intravenous infusion)
Week 8	49.17	48.25	48 ± 4 hours (2 days after completion of the intravenous infusion)
Week 8	120.58	120.25	120 hours ± 1 day (5 days after completion of the intravenous infusion)
Week 9	169.50	168.25	168 hours ± 1 day (7 days after completion of the intravenous infusion) (Week 9)

10.1.1 Summary Table of Alpha ₁ -PI Concentrations (GTI1401 only)		
Population	:	PK population
Contents	:	Alpha ₁ -PI concentrations will be summarized. The summaries will include n, mean (SD), coefficient of variation (%CV) (=SD/Arithmetic mean), median, minimum, maximum as well as geometric mean.
Digit	:	2 decimal places will be displayed for summary table of alpha ₁ -PI Concentrations.
Analysis visit	:	
• Immediately before the intravenous infusion• Immediately after infusion completion (after sodium chloride [NaCl] flush) (0 hour)• 15 minutes after infusion completion• 2 hours after infusion completion• 4 hours after infusion completion• 8 hours after infusion completion• 24±4 hours (1 day after infusion completion)• 48±4 hours (2 days after infusion completion)• 120 hours ± 1 day (5 days after infusion completion)• 168 hours ± 1 day (7 days after infusion completion) (Week 9 Visit) 
Serum concentrations of alpha₁-PI determined by content assay will be presented in a listing by subject, study week, and scheduled or nominal time point.
 
This data listing will provide details of all planned plasma collection time points (scheduled and nominal times as specified in Section 12.1), actual collection date and clock times and elapsed times from the start of the study drug infusion, as well as alpha₁-PI concentrations. Samples excluded from PK analysis will be flagged.
 
The date/clock time for the start and completion of study drug infusion, the actual volume infused, and the actual dose infused (mg/kg) at Week 8 (PK assessment visit) will be presented in a separate listing.

10.1.2 Summary Table of Trough (pre-infusion) Levels (C_{min}) and mean C_{min}	
Population	: 
GTI1401:PK population GTI1401-OLE: Safety population

Contents	: 
This table include following contents.
 
 Summary of trough (pre-infusion) levels (C_{min}) and mean C_{min} at steady state by week number (for C_{min}). Mean C_{min}*calculated by the trough levels. Number and Proportion with mean C_{min} of alpha₁-PI Concentration ≥ 50 mg/dL ($=11.3 \mu M$ nearly equal to $11 \mu M$ which is defined in ATS/ERS statement in 2003). A conversion factor of 0.226 based on the protein only molecular weight of 44.3 KDa for alpha₁-PI is used for converting mg/dL to μM (i.e., 1 mg/dL alpha₁-PI = 0.226 μM). 
No data imputations will be involved in the above concentration data listings, summaries, or figures.
 
Trough (pre-infusion) levels (C_{min}) and mean C_{min} at steady state will be listed

Digit	: 
2 decimal places will be displayed for summary table of C_{min}.

Analysis visit (only C_{min})	: 
GTI1401: Week 1, Week 7, Week 8 and Week 9, *mean C_{min} = Average of C_{min} of each patient measured at Week 7, Week 8 and Week 9 (exclude Week 1)
 
GTI1401-OLE: Baseline (Week 1), and all scheduled visits (Quarterly Visits) starting from Ext Week 12. *mean C_{min} = Average of C_{min} of each patient measured at all scheduled visits (Quarterly Visits) starting from Ext Week 12.

